4.3.3 Pharmacokinetic (PK) Assessments

Blood samples (6 mL each) for measurement of plecanatide and SP-338 concentration will be collected from all patients on Day 1 of the Treatment Period (pre-dose) and at the Week 4 visits. Intensive sampling for formal PK analysis will be conducted in a subgroup of approximately 70 patients (approximately 35 patients per age group) who consent to the additional blood sampling at 30, 60, 90, and 120 minutes following study drug administration on Day 1 of treatment. The actual sampling times will be recorded on the eCRF for each PK sample. The total blood volume collected for PK analysis will be about 12 mL for the majority of patients, and 36 mL for patients participating in the intensive PK analysis. Only samples from patients randomized to active treatment will be analyzed.

Orally delivered plecanatide is not absorbed in the adult population nor is it expected to be absorbed in the 6 to <18-year-old age group. However, should any measurable levels of plecanatide or its primary metabolite (SP-338) be observed, to the extent possible, pharmacokinetic parameter estimates (C_{max} , C_{min} , t_{max}) will be undertaken. Nominal sampling time will be used for all parameter estimation.

In order to maintain the double-blind status of the study, results of the pharmacokinetic assay will be blinded to the investigators, to the sponsor, and monitors during the course of the study.

The procedure for the collection, handling, storage, and shipment of the samples for PK analysis are specified in the site reference laboratory manual.

4.3.4 Vital Signs

The following vital signs will be assessed in accordance with the Schedule of Assessments (**Table 2**). Measurements should be performed when the patient is seated. A clinically significant abnormality at screening may result in the patient being excluded from the study.

- Blood pressure (systolic and diastolic mmHg)

- Heart rate (beats per minute)
- Oral body temperature (°C)
- Respiration rate (breaths per minute)

4.3.5 Electrocardiograms

A standard 12-lead ECG will be performed in accordance with the Schedule of Assessments (**Table 2**). A clinically significant abnormality at Screening, as determined by the PI, will result in the patient being excluded from the study.

4.3.6 Physical Examinations

Physical examinations (PEs) will be performed in accordance with the Schedule of Assessments (**Table 2**). A clinically significant abnormality at Screening may result in the patient being excluded from the study.

The PE at the Screening Visit will be based on the following body systems: general appearance, head (ear, eyes, nose, and throat), cardiovascular, respiratory system, abdomen, musculoskeletal, neurological, lymph nodes, and skin. All other PEs will be symptom-directed.

Neither a urogenital exam or a digital rectal examination is required for the study but should take place at Screening if the Investigator feels that there may be a confounding factor for constipation symptoms e.g., anal pathology, or a rectocele in a female patient.

NOTE: The presence of other alarm symptoms (lower GI bleeding, iron-deficiency anemia, unexplained clinically-significant weight loss and systemic signs of infection or colitis) preclude patient eligibility for this trial, unless the PI has adequately assessed each alarm symptom and has discussed their medical relevance with the Medical Monitor, including the potential need for colonoscopic evaluation of the symptoms.

Height and weight will be measured at the Screening Visit only. BMI calculation will use the height and weight recorded at Visit 1 (Screening Visit).

4.3.7 Concomitant Medications and Diet

Concomitant medications or vitamins/nutritional supplements will be reviewed and documented at each study visit to ensure prohibited/restricted substances are not being taken. Concomitant medication will be documented as described in **Section 3.3**.

Drugs required to be at a stable dose prior to screening including thyroid hormone replacement (30-day stabilization) should not be initiated or dose adjusted during the study.

4.3.8 Rescue Medication

Use of rescue medication will be reported in the electronic diary. Patients will be instructed to take rescue medication only if 72 hours have elapsed since their last BM and reminded of this instruction at each visit.

5. STUDY CONDUCT

5.1 SCHEDULE OF ASSESSMENTS

For the timing of assessments and procedures throughout the study, refer to the Schedule of Assessments **Table 2**. Throughout the study, every reasonable effort should be made by study personnel to follow the timing of assessments and procedures in the Schedule of Assessments for each patient. If a patient misses a study visit for any reason, the visit should be rescheduled as soon as possible.

Table 2 Schedule of Assessments

Study Period Visit Study Week Visit Day (Window)	Screening/ Baseline	Treatment					Post- Treatment Follow-up
		Visit 1 Week -4	Visit 2 Week 1	TC 1 ^a	TC 2 ^a	TC 3 ^a	Visit 3 Week 4 (EOT) or EW
	Day -28	Day 1	Day 3 + 1	Day 7 +3	Day 25 +2	Day 28 +3	Day 42 +3
Informed Consent/Accent	X						
Inclusion/Exclusion Criteria	X	X					
Demography	X						
Medical History (including GI and bowel habits)	X	X					
Prior and Concomitant Medications	X	X	X	X	X	X	X
Physical Examination ^b	X	X				X	X
12-lead Electrocardiogram ^c	X						
Vital Signs ^d	X	X				X	X
Pregnancy Test (urine) ^e	X	X				X	X
Urine Drug Screen for Opioids ^f	X	X					
Serum Chemistry, Hematology, Urinalysis	X	X				X	
TSH (include T3 and T4 only if TSH is abnormal)	X						
PK Sampling: pre-dose and at 28 days(30, 60, 90 and 120 mins post-dose in a subset of 70 patients)		X				X	
Electronic Diary Training and Activation ^g	X						
Diary Eligibility ^h		X					
Randomization		X					
Study Drug Dispensation and Administration ⁱ		X					
In clinic PRO Assessments ^j		X				X	X

Table 2 Schedule of Assessments

Study Period Visit Study Week	Screening/ Baseline	Treatment						Post- Treatment Follow-up
		Visit 1 Week -4	Visit 2 Week 1	TC 1 ^a	TC 2 ^a	TC 3 ^a	Visit 3 Week 4 (EOT) or EW	
	Visit Day (Window)	Day -28	Day 1	Day 3 +1	Day 7 +3	Day 25 +2	Day 28 +3	Day 42 +3
Study Drug Collection and Accountability ^k							X	X
Rescue Medication Dispensation	X	X ^l					X ^l	
Adverse Events ^m	X	X	X	X	X	X	X	X

TC = Telephone Contact; EOT = end of treatment; EW = early withdrawal; EOS = end of study; GI = gastrointestinal; PK = pharmacokinetic; PRO = Patient reported outcome, TSH = thyroid-stimulating hormone.

- a. In addition to on-site clinic visits, study sites will call patients/caregivers on Day 3, Day 7, and as needed to remind them to complete their daily diaries and on Day 25 to remind them to return all unused study drug at their EOT visit.
- b. Physical examination (PE), including body weight measurement, will be performed at Visit 1. A symptom-directed PE will be performed as necessary at Visit 3 (EOT) or EW and Visit 4 (EOS); height is measured at the Screening Visit. Body mass index (BMI) will be calculated by EDC at the Screening Visit only. Height and body weight may be collected at Visit 2 if missed at Screening.
- c. The standard 12-lead ECG will be performed in the semi-recumbent or supine position.
- d. Seated blood pressure, heart rate, respiration, temperature.
- e. Urine pregnancy tests on-site at clinic visits for female patients as per exclusion criteria 5
- f. Urine drug screen for selected opioids (screen includes methadone, morphine and oxycodone) will be performed on-site; a negative result must be confirmed prior to dispensing the study medication.
- g. Clinical site personnel will train patients on the use of electronic diaries at the Screening visit and remind them to make daily entries throughout the study, with retraining as needed. The interactive voice or web response system will provide daily reminders to improve compliance, and as per bullet a, study sites will call patients/caregivers on day 3, day 7, and weekly until Visit 3 (Week 4) to remind them to complete their daily diaries.
- h. Baseline diary results will be reviewed programmatically and a “Diary Eligible” or “Not Diary Eligible” report will be provided to the site immediately prior to randomization.
- i. Patients will take their first dose of study drug at the site on Day 1; it is recommended that for dosing at home, patients take it once daily at approximately the same time in the morning.
- j. Details on timing of each PRO Assessment will be included in the Study Procedure Manual.
- k. Study drug not returned at EOT must be returned at EOS
- l. Only if needed
- m. Adverse Event collection begins immediately after informed consent is signed. A symptom-directed physical examination should be performed as appropriate at discretion of the investigator.

5.2 PROCEDURES BY VISIT

5.2.1 Visit 1: Screening (Day -28)

The patient must be screened within 28 days before the randomization visit in the study. A 3-day window is allowed to complete all procedures of the Screening visit. The last 14 days prior to randomization will be used as the patient's baseline electronic diary assessment.

The following will be completed at the Screening Visit:

- Obtain informed consent/assent. The parent/guardian/LAR must provide written informed consent and the patient must provide written or verbal assent as required by the IRB providing oversight.
- Assign a unique patient number. Unique patient numbers will begin with the clinical site number, e.g., 001 followed by a 3-digit number. Unique patient numbers will be assigned sequentially by the IWRS system accessed by the clinical site personnel. This unique patient number will be kept for the duration of the study. Patients who discontinue from the study before randomization will retain their unique patient number (i.e., numbers from screen fail patients will NOT be reassigned).
- Assess willingness and ability to maintain a stable diet and fiber supplements (if applicable) for the study period and to comply with not using laxatives except for the rescue medication provided as part of the study.
- Determine eligibility, based on Rome IV criteria for child/adolescent IBS and IBS-C. (**Appendix A**)
- Review inclusion/exclusion criteria.
- Collect demographic information.
- Record medical history, including GI and bowel habit history.
- Record prior and concomitant medications, vitamins, nutritional supplements, and dietary history.
- Perform urine pregnancy test for females age 6 to 11 that are of child-bearing potential and all females 12 to < 18.
- Perform urine screen for opioids (see **Section 4.3.2** for details).
- Collect blood and urine samples for safety laboratory tests (serum chemistry, including thyroid-stimulating hormone [TSH], hematology, and urinalysis).
- Measure vital signs (body temperature and seated blood pressure, heart rate, respiration).
- Perform a physical examination, including measurement of body weight and height.
- Perform 12-lead ECG in the semi-recumbent or supine position.
- For a child patient (6 to 11 years of age), determine and document based on the child's level of understanding, whether the child or caregiver will be responsible for recording of diary responses.
- If applicable, document in a source document who the caregiver will be for the duration of the study.
- Train patients/caregivers how to use the electronic diary to record their responses about BM and IBS-C-related symptoms and activate the diary.
- If more than one person will act as the caregiver, e.g., both parents or a parent and an older sibling or grandparent, that person must be trained on diary usage.
- Distribute a laminated card with the BSFS or mBSFS-C to patients/caregivers and explain how to use it to record stool consistency in their daily electronic diaries.
- Ensure patients/caregivers understand the importance of entering data in their diaries daily for all questions.
- Dispense rescue medication to patients and instruct them on appropriate use.

Patients who fail to qualify for randomization during the Screening Period will be considered Screen Failures and the reason for failure will be documented.

Patients who screen-failed may be allowed to re-screen under certain circumstances upon review and approval by the Medical Monitor.

5.2.2 Visit 2: Randomization (Day 1)

Continued study eligibility must be confirmed ***prior to randomization***, including the following:

- Verify Non-Diary eligibility:
 - Review inclusion and exclusion criteria
 - Confirm that patient has used only study-supplied rescue medication laxative (Dulcolax®) since Visit 1
 - Confirmation that patient is on a stable diet and has no significant changes in their consumption of liquids or fiber or their level of activity
 - Perform urine drug screen (a positive test results in automatic screen failure)
 - Perform urine pregnancy test, if applicable (a positive test results in automatic screen failure)
- Update medical history and concomitant medications, as necessary.
- Log into IWRS to obtain system-generated diary eligibility based on the previous 14 days of daily diary entries before randomization. (Only patients who demonstrated diary and RM compliance will be considered diary eligible. **The PI or site staff will not be responsible for evaluating diary data to make the diary-based eligibility determination.**
- Ineligible patients, as determined by the IWRS, will be screen-failed.
- For diary eligible patients, as determined by the IWRS, confirm patient continues to meet all other eligibility criteria and access IWRS to randomize the patient and obtain the study drug kit number.
- The following procedures will be performed ***prior to study drug dosing for patients eligible for randomization***:
- Symptom-directed physical examination and vital signs (body temperature and seated blood pressure, heart rate, respiration rate)
- Assessment of adverse events
- Patient/caregiver to complete all baseline PRO questionnaires (Per Study Procedure Manual) prior to any blood collections
- Collection of blood and urine samples for safety laboratory assessments (hematology, serum chemistry, urinalysis)
- Collection of blood samples for plecanatide/SP-338 concentration assessments (see **Section 4.3.3** for details)
- Selection of drug kit(s) as per the IWRS-generated report
- Supervision of administration of first dose of study drug from the assigned study drug kit(s)
- Recording of time of dosing

The following procedures will be performed ***after study drug dosing***:

- At selected sites and in a subgroup of patients who consented to an additional PK analysis, blood samples will be obtained for PK assessment 30, 60, 90 and 120 minutes after study drug administration
- Dispense the assigned study drug kit(s) (4-week supply) from which the first dose was administered with the instructions for use and storage (as described in **Section 6.4**)
- Instruct patients/caregivers to save all unused study drug and drug packaging for return at Visit 3/Week 4 or EW/ET.
- Distribute additional rescue medication (Dulcolax® tablets), if needed
- Re-emphasize the need for diary compliance, as necessary

- Confirm the next visit and explain the importance of meeting the 3-day window for completion of study visits

5.2.3 Telephone Contact 1 (TC 1): Day 3 to 4

Site personnel will contact patients/caregivers by phone on Day 3 to 4 to review diary compliance ask the following which will be documented in the patient's source record:

- Is the patient taking the study drug as prescribed?
- How is your child feeling?
- Is the daily diary information being entered as instructed?
- Are you/your child experiencing any difficulties with daily diary entry?
- Have there been any changes in concomitant medications?

5.2.4 Telephone Contact 2 (TC 2): Day 7 to 10

Site personnel will contact patients/caregivers by phone on Day 7 to 10 to review diary compliance ask following which will be documented in the patient's source record:

- Is the patient taking the study drug as prescribed?
- How is your child t feeling?
- Is the daily diary information being entered as instructed?
- Are you/your child experiencing any difficulties with daily diary entry?
- Have there been any changes in concomitant medications?

5.2.5 Telephone Contact 3 (TC 3): Day 25 to 27

Site personnel will contact patients/caregivers by phone on Day 25 to 27 to review diary compliance ask the following which will be documented in the patient's source record:

- Is the patient taking the study drug as prescribed?
- How is your child feeling?
- Have there been any changes in concomitant medications?
- Remind participants/caregivers to bring all unused study drug to their next visit.

5.2.6 Visit 3: End of Treatment (EOT) Week 4, Day 28 (+3 days)

The following will be completed at Visit 3:

- Collect/record unused study drug from the supply dispensed at the previous visit
- Review the electronic diary compliance reports and re-emphasize the need for diary compliance throughout the follow-up period
- Have the patient complete the PRO questionnaires (per Study Procedure Manual)
- Assess/record changes in concomitant medications and diet
- Symptoms directed physical examination and vital signs (body temperature and seated blood pressure, heart rate, respiration rate)
- Safety laboratory assessments (hematology, serum chemistry, urinalysis)
- Urine pregnancy test, if applicable
- Collect blood samples for plecanatide/SP-338 concentration assessments
- Assess adverse events
- Distribute additional rescue medication (Dulcolax® tablets), if needed

5.2.7 Visit 4: Week 6, Day 42 (+ 3 days) – End of Study (EOS)

The following will be completed at Visit 4:

- Assess/record changes in physical examination, vital signs, concomitant medications and diet
- Perform urine pregnancy test, if applicable
- Assess adverse events
- Collect/record unused study drug, if not collected (per protocol) at Visit 4
- Have the patient/caregiver complete the PRO questionnaires (per Study Procedure Manual)

5.2.8 Early Withdrawal/Early Termination Visit (EW/ET)

Patients are free to withdraw from participation in the study at any time. Investigators may choose to discontinue a patient's participation in the study if they believe it is in the patient's best interest clinically. If a patient's post-randomization compliance is of concern, contact the medical monitor to discuss. If the patient has an intervening illness that requires discontinuation of study participation, the patient and Investigator will follow procedures for early withdrawal. The following are examples of AEs that qualify for Early Withdrawal (EW):

- A positive pregnancy test will require discontinuation from the study (see **Section 7.7**).
- Changes in laboratory values, PE findings, or other assessments considered by the Investigator (or designee) to be clinically significant will require discontinuation from the study.
- Clinically significant TEAEs, including clinically significant laboratory test abnormalities or SAEs regardless of relatedness to study treatment that cause the patient, investigator, or Sponsor to feel it is not in the patient's best interest to continue.

A patient may also be withdrawn from study drug/study by the Sponsor, regulatory authorities, or the institutional review board (IRB). Patients will also be withdrawn if the entire study is terminated prematurely as described in **Section 9.9**.

Patients who discontinue early from the study should, if possible, have an Early Withdrawal Visit. The Investigator must make every effort (with proper documentation) to have the patient complete this final visit. This visit should take place as soon as possible (and within 5 days) after the patient stops taking study drug.

The following procedures will be performed at the Early Withdrawal Visit:

- Collect/record unused study drug from the supply dispensed at the previous visit
- Have the patient/caregiver complete the PRO questionnaires (see Study Procedure Manual)
- Assess/record changes in concomitant medications and diet
- Symptoms directed physical examination and vital signs (seated blood pressure, heart rate, respiration, and body temperature)
- Safety laboratory assessments (hematology, serum chemistry, urinalysis)
- Perform urine pregnancy test, if applicable
- Collect blood samples for plecanatide/SP-338 assessments
- Assess adverse events.

In all cases, a single, primary reason for withdrawal must be recorded on the eCRF.

Patients withdrawn after randomization will **not** be replaced.

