3.3.2 Prohibited Prior and Concomitant Medications and Supplements

The following medications, laxatives, and supplements are **prohibited within 15 days** prior to the Screening visit and for the duration of the study, unless otherwise indicated:

- Oral anticholinergic agents (topical and inhaled anticholinergics are allowed)
- Drugs with activity at the 5-HT4, 5-HT3, and 5-HT2b receptors
- Antidiarrheal agents including Pepto Bismol™, kaolin, and opiates

- Drugs known to cause diarrhea such as orlistat, acarbose, misoprostol, and colchicine
- Bile acid sequestrants (cholestyramine and colestipol)
- Amitiza® (lubiprostone)
- Linzess®/Constella® (linaclotide)
- Resolor® (prucalopride) antibiotics, including rifaximin, and opioids, including tramadol or opiate antidiarrheals (diphenoxylate, and loperamide) are generally prohibited. However, short-term (< 15 days) use of opioids or antibiotics for the treatment of AEs or intercurrent illness may be administered during the Screening Period prior to Visit 2 (Day 1) or after randomization in the study as long as they are reported. If a patient needs to be started on an antibiotic or a narcotic during the Screening Period, the patient's Visit 2 may be delayed allowing for discontinuation of these medications at least 3 days before randomization.

Prohibited drugs when required and used to treat TEAEs are allowed. The following drugs are allowed only if the patient has been on a **stable dose for the 8 weeks** prior to the Screening/Baseline Period and the patient agrees to remain on this dose for the duration of the study.

- Anticonvulsants
- Antidepressants
- Calcium channel blockers
- Proton pump inhibitors and H2 antagonists
- Antihistamines that have primarily anti H1 activity (e.g., cetirizine, loratadine, and chlorpheniramine)
- Bulking agents (e.g., psyllium [Metamucil®] methylcellulose [Citrucel®], calcium polycarbophil)

Thyroid hormone supplementation: levothyroxine (T4) or natural desiccated thyroid hormone or liothyronine (T3) are allowed only if the patient has been on a stable dose for the 30 days prior to the 4-week Screening/Baseline Period and remains on this dose for the duration of participation in the study. TSH level will be determined at screening to determine eligibility (T3 and free T4 will only be tested if TSH is out of range).

Prohibited Laxatives

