6.3.1 Individual Patient Stopping Criteria

Adverse events due to study drug that affect individual patient safety may necessitate dose interruptions or early discontinuation as described in this section.

Plecanatide therapy in adults with IBS-C and CIC has caused diarrhea in 4% and 5% of patients respectively, with severe diarrhea occurring in 0.7% and 0.6% of patients respectively. Severe diarrhea may cause dehydration. Pediatric patients may be at increased risk for diarrhea and dehydration with plecanatide therapy.

In general, study drug dosing should not be modified for mild diarrhea (Grade 1: increase of < 4 stools per day over baseline) or mild dehydration (Grade 1: dry mucous membranes, diminished skin turgor) (*National Cancer Institute, Common Terminology Criteria for Adverse Events [CTCAE] v5.0, November 27, 2017*). If study drug is not well tolerated by an individual patient, treatment will be permanently discontinued for that patient.

The following guidelines should be used in the case of moderate or severe diarrhea or dehydration:

Table 4 Individual Patient Stopping Criteria

Worst Observed Toxicity Grade NCI Common Toxicity Criteria	Dose Modification for Study Drug
Diarrhea	
Grade 2: Increase of 4-6 stools per day over baseline	No intervention required
Grade 3: Increase of ≥ 7 stools per day over baseline, incontinence, hospitalization indicated	Interrupt study drug for < 7 days until resolved to less than Grade 2 severity. If diarrhea was study drug-related, permanently discontinue study drug. If diarrhea was not study drug-related, e.g., viral gastroenteritis, then consider resuming treatment after consultation with Sponsor's Medical Monitor
Grade 4: Life-threatening consequences, urgent intervention indicated	Permanently discontinue study drug
Dehydration	
Grade 2: IV fluids indicated < 24 hour	Interrupt study drug for < 7 days until resolved to less than Grade 2 severity. If dehydration was study drug-related, permanently discontinue study drug. If dehydration was not study drug-related, consider resuming treatment after consultation with Sponsor's Medical Monitor
Grade 3: IV fluids or hospitalization indicated	Permanently discontinue study drug

Table 4 Individual Patient Stopping Criteria

Grade 4: Life-threatening consequences, urgent intervention indicated	Permanently discontinue study drug
---	------------------------------------

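### Section 5.2.8 does not separate stopping study drug from leaving the study, so a child who stops drug early may lose diary weeks that then count as 0 SBM

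*Combined protocol and SAP*

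**What the plan says.** Protocol 5.2.8 opens with discretion: "Investigators may choose to discontinue a patient's participation in the study" where they judge it clinically best for the patient. The lead-in offers the bullets as examples only. Bullet 2 is firmer: laboratory changes, examination findings or other assessments "considered by the Investigator (or designee) to be clinically significant will require discontinuation from the study". Bullet 3 covers clinically significant TEAEs, laboratory abnormalities and SAEs, but only those "that cause the patient, investigator, or Sponsor to feel it is not in the" patient's best interest to go on.

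The section then treats drug and study as one: "A patient may also be withdrawn from study drug/study by the Sponsor", among others. Of the Early Withdrawal visit, which it calls final, it says: "This visit should take place as soon as possible (and within 5 days) after the patient stops taking study drug". The list of procedures for that visit does not mention the diary.

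Other sections bear on this:

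- **Table 4 (6.3.1)** acts on study drug, not participation. Grade 3 diarrhea and Grade 2 dehydration lead to a pause of less than 7 days. For dehydration it adds: "If dehydration was not study drug-related, consider resuming treatment after consultation with" the Medical Monitor. Unrelated Grade 3 diarrhea is handled the same way.
- **Section 6.3** has the Medical Monitor initiate any interruption under these criteria.
- **Section 3.3.2** makes an exception for short antibiotic and opioid courses, which "for the treatment of AEs or intercurrent illness may be administered during the Screening Period prior to Visit 2 (Day 1) or after randomization".
- **Section 8.3** (PP population) treats stopping study treatment for an adverse event or lack of efficacy as a category of its own.
- **Section 1** has patients keep the diary for two weeks after the last dose and then attend at Week 6.
- **Section 8.4.1 and SAP 3.3.4** assign 0 SBM to any remaining week in which a withdrawn patient has no BM response.

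**The concern.** A child can stop taking tablets and still report bowel movements. If the site reads 5.2.8 as ending participation when drug stops, the diary ends too, and the primary analysis records no bowel movements in weeks that could have been observed. Those zeros say nothing about the child's bowel habit, and withdrawn patients are not replaced. Bullet 2 adds a second problem. It is mandatory, with no grade, relatedness or best-interest condition, while bullet 3 and Table 4 are conditional, and no order of precedence is given.

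**Working it through.** **1. The provisions side by side.** A clinically significant laboratory abnormality falls under bullet 2 (exit required) and bullet 3 (exit if continuing is not in the child's interest). Dehydration shows the clash with Table 4 best. Section 6.3.1 defines Grade 1 by examination findings and in general leaves dosing unchanged, and Table 4 lets a child with unrelated Grade 2 dehydration restart. Bullet 2 covers examination findings of any grade. Neither 5.2.8 nor Table 4 refers to the other.

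**2. When bullet 2 can act.** In the protocol's Table 2, the scheduled laboratory tests, vital signs and examinations after Day 1 fall at Visit 3, Day 28 (+3). The contacts between are telephone calls. (Visit 2 on Day 1 is the visit labelled Week 1.) By Visit 3 the Week 1 to 4 diary, Days 1 to 28, is essentially complete. Only an unscheduled assessment, or Day 1 laboratory results returned after dosing, could trigger bullet 2 earlier.

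**3. Diary coverage after an early stop.** Last dose on Day 7 plus 14 days reaches Day 21. Week 4 is Days 22 to 28 (8.4.2). So even on the generous reading of Section 1, Week 4 is empty and becomes 0.

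**4. The plan's target.** Section 8.2 uses a difference of 1.5 SBM/week, SDs 3.5 and 2.3, and n = 102 and 34. SE = sqrt(3.5²/102 + 2.3²/34) = 0.5251. Power = Φ(1.5/0.5251 − 1.96) = 81.5%, which matches the stated figure at two-sided 5%.

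**5. How many children.** Section 2.1.5 gives adult discontinuations for adverse reactions, in 12-week trials, of 2.5% (IBS-C) and 4.0% (CIC) on drug, and 0.4% and 2.0% on placebo. With 150 active and 60 placebo children:

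- IBS-C rates: 150 × 0.025 + 60 × 0.004 = 3.99
- CIC rates: 150 × 0.04 + 60 × 0.02 = 7.2

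For the narrower conflict of pause versus exit, the adult placebo rates of severe diarrhea (0.1% to 0.3%) can stand in for unrelated events: 210 × 0.001 to 0.003 = 0.2 to 0.6 children. No dehydration rate is given.

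**6. Loss per child.** Let b be baseline SBM/week and c the off-drug change. A zeroed week records −b instead of c, a loss of b + c. Assumptions not in the documents: exit at the end of Week 1, b = 2 to 3, c = 0 to +1, so b + c = 2 to 4. The four-week mean change is used as an approximation to the mixed model.

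**7. Shift in the active-minus-placebo difference** = excess discontinuation rate on drug × loss per child. The excess is 0.025 − 0.004 = 0.021 (IBS-C) or 0.04 − 0.02 = 0.020 (CIC).

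| Diary after exit | Weeks at 0 | Loss per child | Shift, IBS-C rates | Shift, CIC rates | Share of 1.5 |
|---|---|---|---|---|---|
| Stops at exit | 3 | 3(b + c)/4 = 1.5 to 3.0 | 0.032 to 0.063 | 0.030 to 0.060 | 2.0 to 4.2% |
| Two weeks after last dose | 1 | (b + c)/4 = 0.5 to 1.0 | 0.011 to 0.021 | 0.010 to 0.020 | 0.7 to 1.4% |
| Kept to Day 28 | 0 | 0 | 0 | 0 | 0 |

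The shift is toward zero. As an outer bound, eligibility caps baseline at 6 SBM/week. Then b + c = 6 to 7, and the loss when the diary stops is 4.5 to 5.25. The shift is 0.020 × 4.5 = 0.09 to 0.021 × 5.25 = 0.11.

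On power at 102/34, a difference of 1.48 gives Φ(1.48/0.5251 − 1.96) = 80.5%, and 1.44 gives 78.3%.

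**The case against.** The case on the other side is strong on several points.

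- **The protocol is not silent on diaries after dosing.** Section 1 ties two weeks of diary to the last dose, not to Day 28, and Section 4.2.1 runs the diary through the Post-Treatment Period. This stands, and it gives the lower of the two ranges. It does not close the gap: both sections describe the planned course, and Week 4 is still missed after a Week 1 stop.
- **Diarrhea and dehydration arising on treatment are TEAEs**, which bullet 3 addresses conditionally. That is the natural reading for diarrhea, and it leaves dehydration as the clearest conflict.
- **5.2.8 speaks of intervening illness that requires discontinuation**, which implies that other illness does not. This agrees with 3.3.2 and suggests that discretion was intended.
- **The investigator is not powerless under 6.3.** Section 5.2.8 allows discontinuation in the patient's interest, and 6.3.1 requires a permanent stop if drug is not well tolerated. That stands for stopping. For a temporary pause under the stopping criteria, 6.3 names only the Medical Monitor. No safety harm is shown.
- **Off-drug follow-up is a design preference** in a trial that calls itself exploratory. True, but here it is cheap and replaces imputed values with observed ones.

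Two stronger readings are tempting. A reader might infer that bullet 2 turns every abnormal finding into lost primary data; the visit schedule in step 2 shows that it can rarely act in time. A reader might also infer that the wording causes 4 to 7 avoidable exits or biases the comparison. Those counts are ordinary adult discontinuations over 12 weeks, and nothing in the documents attributes any of them to this text.

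**Conclusion.** The point holds as a minor one. Section 5.2.8 blurs stopping drug with leaving the study, and no text secures the diary to Day 28 for a child who stops early, so observable weeks can enter the primary endpoint as zeros. The conflict among bullet 2, bullet 3 and Table 4 is real, but it is mainly a matter of clarity.

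The illustrated effect is about 1 to 4% of the 1.5 target, depending on whether the two-week diary is kept. It rests on adult rates, exit of every such child at the end of Week 1, and assumed values for baseline and off-drug change. Four weeks of treatment would probably give fewer discontinuations than twelve, although 2.1.5 puts most adult diarrhea within the first four weeks and 6.3.1 warns that pediatric risk may be higher. Neither bias between arms in children nor direct harm is demonstrated. Whether zero is the right value for a missing week is a separate question.

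**What to change.** (a) In 5.2.8, state that stopping study drug does not by itself end participation, and that the child continues the daily diary through the planned weeks, at least to Day 28, unless consent or assent is withdrawn.

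(b) In 6.3, state that the investigator may interrupt study drug immediately and then notify the Medical Monitor.

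(c) As clarification, state in 5.2.8 that Table 4 governs diarrhea and dehydration, and make bullet 2 subject to bullet 3's best-interest test.

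No new laboratory stopping rule is proposed. Section 7.3.1 already requires re-evaluation of marked ALT or AST elevations within 48 hours, and nothing here shows that a further drug-stop rule is needed.

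The cost is a short amendment to 5.2.8 and 6.3, brief site retraining, and off-drug diary follow-up of a few children (about 4 to 7 if adult rates carried over). It adds no visits, samples or patients.
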